An adverse event (AE) is any untoward medical occurrence in a subject participating in an investigational study or protocol regardless of causality assessment. An adverse event can be an unfavorable and unintended sign (including an abnormal laboratory finding), symptom, syndrome or disease deemed to be possibly related to or occurring during the use of an investigational product.

Serious adverse events (SAE) are adverse events occurring at any dose which meet one or more of the following serious criteria:

- Results in death (i.e. the AE caused or lead to death)
- Is life-threatening (i.e. the AE placed the subject at immediate risk of death; it does not apply to an AE which hypothetically might have caused the death if it were more severe)
- Requires or prolongs inpatient hospitalization (i.e. the AE required at least a 24-hour inpatient hospitalization or prolonged a hospitalization beyond the expected length of stay; hospitalizations for elective medical/surgical procedures, scheduled treatments, or routine check-ups are not SAEs by this criterion)
- Is disabling (i.e. the AE resulted in a substantial disruption of the subject's ability to carry out normal life functions)
- Is a congenital anomaly/birth defect (i.e., an adverse outcome in a child or fetus of a subject exposed to the study drug prior to conception or during pregnancy)
- It does not meet any of the above serious criteria but may jeopardize the subject and may require medical or surgical intervention to prevent one of the outcomes listed above

When assessing causality, the investigator should determine the association and consider if there is a clinically plausible time sequence between onset of the AE and the associate drug administration; and/or there is a biologically plausible mechanism for the drug causing or contributing to the AE; and the AE cannot be attributed solely to concurrent/underlying illness, other drugs, or procedures.

Expected adverse events are those adverse events that are listed or characterized in the Package Insert. Unexpected adverse events are those not listed in the Package Insert or not identified. This includes adverse events for which the specificity or severity is not consistent with the description in the Package Insert.

Unexpected adverse events grade 3, 4 and 5 as well as any medical event equivalent to CTC Grade 3, 4 or 5, which precipitated hospitalization (or prolongation of existing hospitalization) will be reported regardless of designation as expected or unexpected, along with attribution, to [name] pager at [contact] **within 24 hours**. These reportable adverse events will also be documented on a Medwatch 3500A form supplied by the coordinating center. The Medwatch 3500A form will be submitted to [name] within the time frame specified under AE Reporting Guidelines (on page 24) via fax to [contact] – use a FAX cover page.

Expected adverse events grade 4 and 5 will be reported on a study supplied Medwatch 3500A form **within 5 working days or 10 calendar days, whichever is sooner**. (use study supplied Medwatch 3500A form).

[name], who will discuss the adverse event with the local principal investigator (PI), will ensure that the Medwatch form has been obtained and the adverse event reported to the independent reviewer, [name], who has been designated as independent data safety medical monitor. [name], Director of Research at Maine Center for Cancer Medicine will review incoming adverse event information and any data in real time. The local principal investigator or treating physician along with [name], will determine if an AE is treatment related. [name] will review and evaluate all incoming events for causality and may discuss the events with all the PIs. [name] will review attribution and causality and may disagree with the previous determination. Documentation of his review and any of the previous reviews will be forwarded to the bi-monthly Pediatric Solid Tumor Board. [name] has the authority to determine if an adverse event requires the study to be discontinued or be put on hold. If this occurs, all participating sites will be notified immediately as well as the MMC IRB. All sites are expected to inform their local IRB.

In addition, patients enrolled to this study will be regularly discussed as a part of the bi-monthly Pediatric Solid Tumor Board. The discussion will include tumor response, toxicity and reported adverse events. A copy of all adverse event documentation and a summary of the discussion between [name] and independent reviewer will be given to the Tumor board. The bi monthly Pediatric Solid Tumor Board Conference has the authority to determine if an adverse event requires the study to be discontinued or put on hold. A Data and Safety Monitoring worksheet will be completed at this conference.

The descriptions and grading scales found in the revised NCI Common Toxicity Criteria (CTC) version 4.0 (<http://ctep.cancer.gov/reporting/ctc.html>) will be utilized for adverse event reporting. All appropriate treatment areas should have access to a copy of the CTC version 4.0.

A table showing the **expected** adverse events specific for each of the agents is found below.

Expedited Adverse Event Reporting

*Expedited Reporting Guidelines – (including **hospitalization** defined in bullet 1 below)*

Adverse Event Reporting Guidelines

Unexpected Event Grade 3, 4 and 5	Expected Event Grade 3	Grade 4 and 5
Report by phone to MMC/MCCP Coordinating Center [name] at [contact] within 24 hrs. Written expedited Medwatch Form 3500A report to be faxed to [contact] within 48 hours.	Adverse Event Expedited Reporting NOT required.	Written Medwatch 3500A report, within 5 working days or 10 calendar days, whichever is sooner.
This includes all deaths within 30 days of the last dose of sirolimus treatment regardless of attribution.		This includes all deaths within 30 days of the last dose of sirolimus treatment regardless of attribution.
Any late death attributed to sirolimus (possible, probable, or definite) should be reported within 48 hours of site's knowledge by phone and Medwatch form per above.		Any late death attributed to sirolimus (possible, probable, or definite) should be reported within 48 hours of site's knowledge by phone and Medwatch form per above.

For Hospitalization only – Any medical event equivalent to CTC Grade 3, 4, or 5, which precipitated hospitalization (or prolongation of existing hospitalization) must be reported regardless of designation as expected or unexpected and attribution.

Written reported procedures:

- A completed MedWatch form will be utilized for collecting adverse event information. Complete in the timeframe specified in guidelines above and fax to [contact] to the attention of [name]. In addition each site must report adverse events per their local IRB policy.

All delinquent reporting to the MMC/MCCP coordinating center must include documentation of reason for delinquency and may require implementation of an action plan.

Records, Reporting, and Study Monitoring –

Data Collection Forms:

Forms should be completed at specified time points and sent to:

[name]
Coordinator of Clinical Research
Maine Children's Cancer Program
[name]
[name]
[contact]
[contact]
Email- [contact]

Monitoring of Study Data:

As the coordinating center MMC/MCCP will monitor and review all data for accuracy and completeness, and will collect data quarterly. Queries will be generated to clarify unclear or missing data. Records of this review will be maintained at MMC/MCCP. Eligibility, deviations, adverse events and essential data elements will routinely be verified. As the coordinating center MMC/MCCP will obtain a copy of each local sites IRB approval and IRB approved informed consent documents and all subsequent IRB reportable changes. On an annual basis a random review of 20% of the data not previously reviewed will be performed.

Unidentified patient SAE data will be shared w/ Pfizer.

STATISTICAL ANALYSIS

Primary Objective

The primary scientific endpoint for patients enrolled on this pilot study is determine whether mTOR pathway activation decreases in patients with surgically-resectable desmoid tumor that is removed following pre-operative treatment with sirolimus. We anticipate finding that 4 weeks of sirolimus will result in decreased mTOR pathway activation, assessed using immunohistochemical (IHC) studies outlined above. IHC results after 4 weeks of sirolimus, scored on a scale of 0-12, from patients enrolled on the study will be compared with archived tumor samples from untreated patients using a two-sample t-test. The sample size of n=15 trial patients and n=50 historical controls will provide 80% power to detect a true difference in means of 2.6 points on the 12-point scale. While the t-test is fairly robust, if the data are highly non-normally distributed a nonparametric, rank-sum test will be applied instead. In addition, responses will be dichotomized as described above (negative <3, positive >4) and the

proportion positive compared between the two groups using Fisher's exact test. Finally, pre- and post-treatment values within patients enrolled on the trial will be compared using paired t or Wilcoxon, signed-rank tests.

Secondary Objectives

These scientific endpoints will be mostly exploratory, given the small numbers of patients enrolling in this pilot study. Nonetheless, we anticipate finding that 4 weeks of sirolimus will result in decreased tumor-associated pain. Pain assessments will be made using validated age-based pain assessment scales and compared pre- and post-treatment using a paired t test. Descriptively, the number of patients showing >50% improvement in their pain score, worsening pain, or between 0 and 50% improvement will be tabulated. Having decreased pain in approximately 60% of patients without substantial toxicity will be viewed as a success.

Patients will also be followed for recurrence post-surgery. As a benchmark, in a similar cohort of patients treated on the Pediatric Oncology Group 9650 study with vinblastine and methotrexate, the progression-free survival rate at 1 year was 58%. Vinblastine and methotrexate, which most would agree represents the current standard of care for desmoid tumor that is not amenable to surgery or radiation, is associated with significant toxicity: 18 of 27 (66%) patients on that trial experienced NCI grade 3 or 4 toxicity. Having histochemical evidence for decreased mTOR pathway activation with less toxicity will be viewed as a success, and lead the investigators to explore ways to test sirolimus in a randomized, phase II study in which the drug is used for patients with unresected disease and for patients in which the drug is continued following surgical resection of disease.

An independent statistician has been recruited from Center for Outcomes Research and Evaluation (CORE) at Maine Medical Center Research Institute. [name], assisted in the original presentation of this project. There will be no interim analysis performed; analysis will be performed at study completion. If [name] is not available, [name]. Senior Biostatistician at CORE, will be the lead statistician for this project. [name] will be assuming the analysis or consulting on this project as this is her area of expertise and her background is in translational research.

Early Stopping Rules

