The threshold creatinine values in this Table were derived from the Schwartz formula for estimating GFR (Schwartz et al. J. Peds, 106:522, 1985) utilizing child length and stature data published by the CDC.

- Hepatic
 - Adequate liver function defined as:
 - Total bilirubin \leq 1.5 x upper limit of normal (ULN) for age, and
 - SGPT (ALT) \leq 2.5 x upper limit of normal (ULN) for age.
- Hematologic function
 - Adequate bone marrow function defined as:
 - ANC \geq 1×10^9 /L
 - Hemoglobin \geq 10g/dL
 - Platelet count \geq 100×10^9 /L
- Female patients must have a negative pregnancy test.
- Female patients who are lactating must agree to stop breast-feeding.
- Sexually active patients of childbearing potential must agree to use effective contraception.
- Patients must be able to cooperate fully with all planned protocol therapy.
- Signed informed consent MUST be obtained from patient or parent/legal guardian (if patient is <18 yrs of age). Consent must be obtained prior to any study procedures and study entry.

Exclusion criteria

- Patients with other fibroblastic lesions or other fibromatoses are NOT eligible.
- Concomitant medications restrictions:
 - a) Patients may NOT have received prior mTOR inhibitors.
 - b) Growth factor(s): Must not have received within 1 week of entry onto this study.

- Patients must not be known to be HIV positive. Testing for HIV is not mandatory.
- Patients must not be taking medicines known to influence sirolimus metabolism (see Table on Page 15).

Regulatory

- All patients and/or their parents or legal guardians must sign a written informed consent.
- All institutional, FDA, and NCI requirements for human studies must be met.
- As the coordinating center MMC/MCCP will obtain a copy of each local sites IRB approval and IRB approved informed consent documents and all subsequent IRB reportable changes.

REGISTRATION PROCEDURES

All eligible subjects that provide consent to this study will be registered at MMC/MCCP. Eligibility will be verified with the Investigator or treating physician prior to registering the subject to study.

REQUIRED OBSERVATIONS

Tumor evaluation must be completed within 21 days prior to study entry. In addition, labs and physical exam must be completed within 7 days prior to study entry. Therapy must begin within 21 days following signing informed consent document.

Other recommended and required observations are detailed in the following Tables:

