Evaluations	Prior to Study Entry*	During Course 1**	Prior to Surgery*
History	X	Weekly	
Physical Exam (HT, WT, BSA, VS)	X	Weekly	X
Performance Status	X		
Pain Scale ¹	X	Weekly (required)	X
CBC, differential, platelets	X	Weekly	X
Serum electrolytes including Ca++, PO4, Mg++	X	Weekly	X
Creatinine, SGPT, bilirubin	X	Weekly	X
Fasting Glucose/Cholesterol/Triglyceride	X	Prior to week 3	X
Urine Pregnancy Test ²	X		
Urinalysis	X		
Trough Sirolimus Level		Weekly	
MRI of Primary ³	X		X ⁴

* All evaluations required except where noted.

** Course 1 represents the first 4 weeks of sirolimus; all evaluations strongly recommended except where otherwise noted. ¹

Patients ≥ 3 and < 10 years of age will use the Wong-Baker FACES scale; patients who are ≥ 10 years of age will use the numeric scale. See Appendix 1.

² Patients of childbearing potential require a negative pregnancy test prior to starting treatment.

³ MRI should include images in at least two planes with (a) pre-contrast images with the following pulse sequences (1) T-1 weighted, (2) fast spin echo T-2 weighted with fat saturation OR a short tau inversion recovery (STIR); and (b) post-contrast images with T-1 weighted pulse sequence with fat suppression.

⁴Optional but strongly recommended. If performed, attempt to obtain as close to planned surgery as possible.

Post-surgery follow-up evaluation – months post therapy

Evaluations post-Surgery*	3	6	9	12	18	24	36
History	x	x	x	x	x	x	x
Physical Exam (HT, WT, BSA, VS)	x	x	x	x	x	x	x
MRI of Primary	x	x	x	x	x	x	x
Data Collection Forms ¹ (required)	x	x	x	x	x	x	x
Operative Report (required)	x						

* All evaluations strongly recommended except where otherwise noted.

¹See Case Report Forms

TREATMENT PLAN

Preoperative Chemotherapy for all patients

- Sirolimus:
 - Loading dose of 12 mg/m²; PO day 1 (**MAX dose 12 mg**)
 - Starting 24 hours after the initial loading dose, patients will receive a dose of 4 mg/m² daily; PO days 2 through 28 (**MAX dose 4 mg/day**)

If the patient suffers any Grade 3 or 4 toxicity that the treating physician feels may delay surgery, the patient will come off study.

Surgical Resection for all patients

- Sirolimus will be discontinued following 28 days of therapy. Surgical resection should be accomplished within 3 days of completing therapy. The tumor will be processed for routine histology as well as for study specific tests.

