- Anticipated or unanticipated surgical delay beyond 3 days should be discussed with the study PI to determine if a patient should be removed from protocol therapy.

Note about Postoperative Chemotherapy

- *The pilot study is complete following tumor resection. If the treating physician chooses to continue sirolimus following resection, for example, based on symptomatic improvement, it will be independent of this clinical trial.*

DRUG ADMINISTRATION GUIDELINES:

- **Sirolimus**
 - Prior to beginning and each week, the following laboratory criteria must be met before beginning or continuing Sirolimus:
 - ANC $\geq 0.75 \times 10^9/L$
 - Platelets $\geq 75 \times 10^9/L$
 - Serum creatinine $\leq 2 \times$ baseline or GFR $\geq 70 \text{ mL/min}/1.73 \text{ m}^2$
 - Total bilirubin 0 – 21 $\mu\text{mol/L}$ (0 -1.24 mg/dL)
 - Sirolimus is to be administered daily by mouth.
 - The drug may be given without regard to food, but should be consistently administered the same way (with or without food).
 - The oral solution may be diluted in 2 ounces of water or orange juice immediately prior to administration. The glass should be rinsed with an additional 4 ounces of the same fluid and administered to the patient.
 - Dose adjustments will not be made based on trough levels.

DRUG MODIFICATIONS FOR TOXICITY

If the patient suffers any Grade 3 or 4 toxicity that the treating physician feels may delay surgery, the patient will come off study.

Dose Modifications for Sirolimus

Toxicity	Criteria/Grade	Action												
Myelosuppression	ANC < 0.75 x 10 ⁹ /L Plts < 75 x 10 ⁹ /L	Withhold sirolimus, and repeat within 3-4 days until neutropenia or thrombocytopenia are resolved. If no previous delay, resume at full dose. If previous delay, reduce dose by 25%.												
Mucositis, Severe Abdominal Pain, Diarrhea	Grade 4 mucositis or repeated Grade 3 mucositis	Delay until resolved and decrease subsequent sirolimus dose by 25%.												
Renal Toxicity	Serum creatinine > 2 x baseline or GFR < 70 mL/min/1.73 m ²	Delay for one week and decrease subsequent sirolimus dose by 25%. If renal function does not improve, discontinue sirolimus.												

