Hepatic Toxicity	Raised Total Bilirubin	Reduce sirolimus as follows: 

Bilirubin Concentration	% Dose	

0 – 21 µmol/L (0 -1.24 mg/dL)	100%	

22 – 35 µmol/L (1.25-2.09 mg/dL)	75%	

36 – 52 µmol/L (2.1 -3.05 mg/dL)	50%	

53 – 86 µmol/L (3.06-5.0 mg/dL)	25%	

> 87 µmol/L (> 5.0 mg/dL)	0%	

	Bilirubin Concentration	% Dose	0 – 21 µmol/L (0 -1.24 mg/dL)	100%	22 – 35 µmol/L (1.25-2.09 mg/dL)	75%	36 – 52 µmol/L (2.1 -3.05 mg/dL)	50%	53 – 86 µmol/L (3.06-5.0 mg/dL)	25%	> 87 µmol/L (> 5.0 mg/dL)	0%
Bilirubin Concentration	% Dose													
0 – 21 µmol/L (0 -1.24 mg/dL)	100%													
22 – 35 µmol/L (1.25-2.09 mg/dL)	75%													
36 – 52 µmol/L (2.1 -3.05 mg/dL)	50%													
53 – 86 µmol/L (3.06-5.0 mg/dL)	25%													
> 87 µmol/L (> 5.0 mg/dL)	0%													

Other Toxicity:

Any other persistent grade 3 or 4 toxicity should be discussed with the Study co-PIs and decided on a case by case basis. Common Terminology Criteria for Adverse Events (CTCAE) version 4 will be used for toxicity assessment. Please see Adverse Event and Data Reporting for guidelines for submitting AdEERs forms to the NCI for other grade 4 toxicities.

AGENT INFORMATION

Sirolimus (Rapamune®, Rapamycin)

Supplier:

Commercially available as Rapamune® oral solution 1mg/mL and 0.5mg, 1mg, and 2mg tablets.

Pharmacology:

Sirolimus inhibits T-lymphocyte activation and proliferation that occurs in response to antigenic and cytokine (Interleukin (IL)-2, IL-4, and IL-15) stimulation by a mechanism that is distinct from that of other immunosuppressants. Sirolimus also inhibits antibody production. Sirolimus binds to the immunophilin, FK binding protein-12 (FKBP-12). Sirolimus suppresses cytokine driven T-cell proliferation, inhibiting the progression from the G1 to the S phase of the cell cycle.

Formulation:

The 1 mg/mL oral solution must be refrigerated and protected from light. 0.5mg, 1mg, and 2mg tablets.

Stability:

Once the bottle is opened, the solution is stable for 30 days. The individual oral solution pouches are stable at room temperature for 24 hours. The bottles of oral solution are stable at room temperature for 15 days.

Guidelines for Administration:

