Sirolimus is to be taken by mouth. Doses should be given every 24 hours +/- 2 hours. The drug may be given without regard to food, but should be consistently administered the same way (with or without food). The oral solution may be diluted in 2 ounces of water or orange juice immediately prior to administration. The glass used should be rinsed with an additional 4 ounces of the same fluid and administered to the patient.

Potential toxicities:

	Common (21-100% Frequency)	Occasional (5-20% Frequency)	Rare (<5% Frequency)
Immediate: Within 1-2 days of recovery drug	Nausea, Vomiting	Rash	Angioedema
Prompt: Within 2-3 weeks, prior to next course.	Diarrhea Hypertension Increased Creatinine	Infections (e.g. nasopharyngitis); Edema; Weight Gain, Arthralgia; Tremor; Acne; Myelosuppression; Abdominal Pain; Fatigue; Myalgia; Chest Pain; Dizziness; Hypokalemia; Hypophosphatemia; Hyperglycemia (diabetes mellitus)	Hepatotoxicity
Delayed: Anytime after above.	Hypercholesterolemia, Hypertriglyceridemia	Stomatitis, Wound Complications	Hirsutism, Secondary Lymphoma, Pulmonary Hemorrhage Interstitial Lung Disease
Late: Anytime after completion of treatment			

TABLE OF CLINICALLY RELEVANT DRUG INTERACTIONS FOR CYP3A4, 5, Or 7

SUBSTRATES	INHIBITORS	INDUCERS
Macrolide antibiotics: clarithromycin erythromycin NOT azithromycin Telithromycin	HIV Antivirals: delavirdine indinavir nelfinavir ritonavir Other: amiodarone aprepitant NOT azithromycin chloramphenicol cimetidine clarithromycin diethyl-dithiocarbamate diltiazem erythromycin fluconazole fluvoxamine gestodene grapefruit juice itraconazole ketoconazole mifepristone nefazodone norfloxacin norfluoxetine mibepradil star fruit verapamil voriconazole	HIV Antivirals: efavirenz nevirapine Other: barbiturates carbamazepine glucocorticoids modafinil phenobarbital phenytoin rifampin St. John's wort troglitazone oxcarbazepine pioglitazone rifabutin
Anti-arrhythmics: alprazolam diazepam midazolam triazolam		
Immune Modulators: cyclosporine tacrolimus (FK506)		
HIV Protease Inhibitors: indinavir ritonavir saquinavir		

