Note: Predictions of drug interactions due to an effect on PGP transport is limited by the fact that drugs may be metabolized by multiple pathways, offering an alternative elimination route; the sum of the multiple drug effects on PGP is unknown; and PGP activity is influenced by non-drug entities such as: inflammation, irradiation, etc.

Adapted from Lexi-Comp's Drug Interaction Handbook 2nd edition 2004

CRITERIA FOR REMOVAL FROM PROTOCOL THERAPY AND OFF STUDY CRITERIA

Criteria For Removal From Protocol Therapy

- Progressive disease
- Dose-limiting toxicity
- Patient withdrawal from protocol
- A delay in surgery > 7 days from the completion of sirolimus
- Patient missed >25% of sirolimus doses

Patients who are off protocol therapy are to be followed until they meet the criteria for off study (see below). Follow-up data will be required.

Off Study Criteria

- Death
- Lost to follow-up
- Patient withdrawal of consent for study follow-up

PATHOLOGY GUIDELINES

Pre-study pathology:

Pre-Study tumor or biopsy sample will be analyzed for confirmation of diagnosis and for immunohistochemical analysis for mTOR pathway activation.

To accomplish this, representative H and E-stained sections and six (6) unstained, 5 micron sections on positive-charged slides, cut from the same block will be submitted. If slides cannot be sent, blocks would be acceptable.

Pathology of the specimen after neo-adjuvant chemotherapy:

Immunohistochemical studies for mTOR pathway activation will be performed on the resected tumor samples. Immunostaining results will be compared to a cohort of previously untreated, archived specimens, and also paired pre-treatment tumor or biopsy specimens if available. (See more below in Statistical Analysis.)

To accomplish this, representative H and E-stained sections and ten (10) unstained, 5 micron sections on positive-charged slides, cut from the same block will be submitted. If slides cannot be sent, blocks would be acceptable.

Pathology specimens should be sent within 3 weeks of enrollment to:

[name]
UCLA Department of Pathology
Bone, Soft Tissue and GI Pathology
Director, Translational Pathology Core Laboratory, 13-145 CHS
[name]
[contact]
[contact]

Histological Assessment

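### The weekly bilirubin limit forbids sirolimus doses that the hepatic toxicity table orders; a lesser inconsistency is that surgery-delaying toxicity is called off study rather than removal from protocol therapy

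*Combined protocol and SAP*

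**What the plan says.** **Bilirubin.** Drug Administration Guidelines lists laboratory values to be checked before the first dose and weekly: "the following laboratory criteria must be met before beginning or continuing Sirolimus". The total bilirubin entry is 0–21 µmol/L (0–1.24 mg/dL). The hepatic row of Dose Modifications for Sirolimus gives a different instruction for a raised value, "Reduce sirolimus as follows", followed by five bands running from 100% of dose down to 0%. The daily dose is 4 mg/m² with a maximum of 4 mg (Treatment Plan).

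**Disposition.** Treatment Plan and Drug Modifications for Toxicity carry the same sentence: "If the patient suffers any Grade 3 or 4 toxicity that the treating physician feels may delay surgery, the patient will come off study". The section on removal from protocol therapy and off-study criteria keeps two separate lists. Removal from protocol therapy includes "Dose-limiting toxicity" and a surgical delay of more than 7 days; those patients stay in follow-up, and their data are required. The off-study list has three entries: death, loss to follow-up, and withdrawal of consent for follow-up. Treatment Plan also sends a surgical delay beyond 3 days to the study PI "to determine if a patient should be removed from protocol therapy".

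**The concern.** A site holding a weekly bilirubin result of 22–86 µmol/L has two written instructions and cannot follow both. One says the condition for continuing has failed. The other says to continue at a reduced dose. The trial is multi-site, so the same value could lead to different treatment in different places, and whichever choice a site makes departs from one instruction. This is a dosing rule in children and young adults, so it should have a single answer.

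The disposition wording matters less. The protocol separates stopping treatment from leaving the study, and the surgery-delaying toxicity sentence uses the second term for an event that looks like the first. A site that takes the sentence literally could stop sending the follow-up from which recurrence is assessed.

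**Working it through.** The plan states no figure on this point to reproduce. The check sets the rules side by side.

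**Bilirubin.** Inputs: the weekly limit (Drug Administration Guidelines), the five bands (Dose Modifications for Sirolimus, hepatic row) and the 4 mg/day cap (Treatment Plan). The cap is reached at a body surface area of 1 m², since 4 mg/m² × 1 m² = 4 mg. The table dose at the cap is the percentage × 4 mg.

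| Bilirubin, µmol/L (mg/dL) | Table dose | At the cap | Weekly limit | Agree? |
|---|---|---|---|---|
| 0–21 (0–1.24) | 100% | 4 mg | met | yes |
| 22–35 (1.25–2.09) | 75% | 0.75 × 4 = 3 mg | not met, 0 mg | no |
| 36–52 (2.1–3.05) | 50% | 0.50 × 4 = 2 mg | not met, 0 mg | no |
| 53–86 (3.06–5.0) | 25% | 0.25 × 4 = 1 mg | not met, 0 mg | no |
| above 87 (above 5.0) | 0% | 0 mg | not met, 0 mg | yes |

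Three of five bands conflict at a weekly check. A value of 1.5 mg/dL falls in the second band: 3 mg under the table, none under the weekly limit. Units do not explain the difference. At 17.1 µmol/L per mg/dL, 21 µmol/L is 1.23 mg/dL, and the 0–21 band is written identically in both places.

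The neighbouring rows do not supply a precedence rule. The myelosuppression row withholds sirolimus below the same neutrophil and platelet limits as the weekly list (0.75 and 75 × 10⁹/L). The renal row delays drug for one week when its limit is crossed. Only the bilirubin row keeps dosing after the weekly limit has failed.

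**Disposition.** Of the three off-study criteria, none is a toxicity or a surgical delay. Both appear, in some form, among the reasons for removal from protocol therapy. Follow-up data forms are required at 3, 6, 9, 12, 18, 24 and 36 months, which is 7 time points. Early Stopping Rules expects surgery-delaying Grade 3 or 4 toxicity in no more than 1 of 15 patients. The forms at stake are therefore 0 × 7 = 0 to 1 × 7 = 7.

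**The case against.** **Bilirubin.** The best defence is that 0–21 µmol/L is also the table's 100% band, so the weekly list can be read as the full-dose condition and the table as the rule once it is exceeded. Many clinicians would read it that way. But the weekly list speaks of continuing, not of full dose, and the blood-count and renal rows do stop drug at their limits. The reading is plausible and unstated. It is also fair that the limit applies at the weekly check, so a value drawn between checks could fall under the table without conflict.

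**Disposition.** A reader might infer that the off-study list is closed and that the toxicity sentence flatly contradicts it. The documents do not go that far. The list does not say that only these three reasons apply, so the sentence could be adding a fourth. Dose-limiting toxicity is not defined, and a delay of more than 7 days is a realised event, whereas the sentence concerns a physician's judgement that toxicity may delay surgery. What stands is inconsistent terminology that can be acted on in two ways. The toxicity itself is still reported, including deaths within 30 days of the last dose and later deaths attributed to sirolimus.

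**Conclusion.** The bilirubin conflict is real and should be fixed. At the 4 mg/day cap the two rules differ by 3, 2 or 1 mg/day, depending on the band. How many patients would be affected cannot be derived: the drug table lists hepatotoxicity as rare, but that is not a rate of bilirubin above 1.24 mg/dL. The disposition wording is minor: 0–1 of 15 patients, bearing on recurrence, a secondary and mostly exploratory endpoint. That count assumes that toxicity a physician thinks may delay surgery is about as rare as toxicity that does delay it.

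Four stronger readings are not supported:

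- **Damage to the primary analysis or power.** Nothing in either conflict enters the comparison of 15 patients with 50 archived specimens or its stated power, and no such effect is claimed.
- **Removal under the missed-dose rule** ("Patient missed >25% of sirolimus doses"). A one-week hold is 7 of 28 doses, 25.0%, which does not exceed the limit. Going beyond it needs a longer hold and needs withheld doses to count as missed. The protocol sets no hold length for bilirubin and does not say how withheld doses are counted.
- **A clash with eligibility**, which allows bilirubin up to "1.5 x upper limit of normal (ULN) for age". The ULN is not given, and being eligible and being ready to start are separate checks.
- **A renal contradiction.** The weekly and toxicity criteria can diverge when creatinine and GFR disagree, but a site can satisfy both by holding.

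**What to change.** 1. In Drug Administration Guidelines, keep total bilirubin of 0–1.24 mg/dL as the criterion for starting. Replace the weekly bilirubin criterion for continuing with an instruction to dose according to the hepatic toxicity table and to hold above 5.0 mg/dL.
2. In Treatment Plan and in Drug Modifications for Toxicity, change the consequence of Grade 3 or 4 toxicity that may delay surgery from coming off study to being removed from protocol therapy, so that the follow-up requirement applies.

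Both are wording edits that fit in one amendment. They add no visits or tests: bilirubin is already on the weekly schedule and the follow-up forms are already required.
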